The two arm cluster RCT will compare the effects of task-shifted, evidence-based depression care vs. usual care on adherence to each step of the PMTCT care cascade at 8 ANC clinics in Uganda. At 4 experimental sites, task-shifted, depression care will include (1) depression screening and psychoeducation, (2) depression diagnosis, and (3) provision of evidence-based problem solving therapy (PST), or antidepressant therapy (ADT) for those with severe and refractory depression (or who decline PST), to be implemented by trained peer mothers and midwife nurses. The 4 control sites will use usual care services for managing depression, which consist of the FSG program and referrals to a mental health specialist. At each site, 50 HIV+ newly pregnant women (total n=400) who screen positive for potential depression will be enrolled and followed until 18-months post-delivery to assess how depression and depression alleviation relate to primary (adherence to each component of the PMTCT care continuum, maternal virologic suppression) and secondary (infant HIV status; post-natal maternal and child health outcomes) outcomes, as well as processes of depression care (treatment uptake and depression alleviation among clinically depressed patients). The PST/ADT treatment will be provided only to study participants, not all depressed clients, because our focus is the effects of depression treatment on PMTCT adherence and pregnancy outcomes, not implementation research for scaling

up the model in ANC care (with HIV and non-HIV women), which is a much broader focus. A cost-effectiveness analysis will be used to compare the two study arms.

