Primary Aim 1: intervention effects on primary outcomes. We will use logistic regression to test for differences between the two study arms on (i) PMTCT adherence, coded as a binary variable, at each stage of the PMTCT care continuum, and (ii) maternal viral suppression. The regression models will include patient characteristics such as age, CD4 and HIV disclosure status that may explain variance in observed differences. We will also explore significant interactions between the covariates and study arm to assess which patient types are likely to be adherent and virally suppressed in depression care vs. usual care. The effect of depression care on PMTCT adherence will be examined using intention to treat as the primary approach. We will use a repeated-measures model that will allow us to incorporate correlation in measurements of each person over time. The sample size of individuals for such models is adequate. The model formulation is: $\text{adherence}_{it} = \alpha + \beta G_i + \gamma(t) + \delta G_i \times t + \theta_i + \varepsilon_{it}$ where i is individual, t is continuous time, G is binary indicator of treatment group, β allows for baseline differences between the two groups, γ is the time trend in the outcome common to both groups, and δ is the interaction of treatment group and time, and shows the intervention effect (i.e. effect of depression care relative to usual care). Further, θ_i is an individual-level random effect (to allow for variation across participants) and ε_{it} is time period-specific error. With a vector of individual-level covariates X_i included in the model, we can assess main effects of patient characteristics and interactions between these X_i and indicator of treatment group. Such a model will allow us to test for significance of potential mediators: e.g., do effects of the depression care model vary by the patient's physical health at baseline? As the primary approach is intention-to-treat, the estimates will capture the average benefit for depressed patients, regardless of compliance or use of depression treatment. A secondary "completers only" analysis will be conducted as well. In addition, we will conduct a dose-response type analysis to explore the relationship between continuous implementation variables (e.g. treatment sessions attended), which are collected for all participants, and primary outcomes. Further, to better understand how or why the intervention exerted its effect, we will model the relationship

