between fidelity measures (e.g. quality) and primary outcomes, as well as conduct mediation analysis including fidelity as a mediator, in the subgroup of patients enrolled in clinics receiving the intervention arm (depression care).

Secondary Aims 1 & 2: Explore relationship of depression and depression alleviation with primary and secondary outcomes. *Hypothesis: Depression will be associated with lower adherence to each step of the PMTCT care continuum, maternal viral suppression and maternal and child health, while depression alleviation will be associated with better adherence, viral suppression and health outcomes.* We will conduct (unadjusted) bivariate analysis to initially examine significant associations between baseline depression ($EPDS \geq 13$) and depression alleviation over time with the primary and secondary outcome measures. Next, longitudinal analysis will be conducted to incorporate repeated observations of individuals and to explore the relationship between change in depression and outcomes over time, and to test whether depression alleviation ($EPDS \leq 6$) is related to change in these outcomes. Models will control for observed individual characteristics and unobservables through a random effect term to incorporate characteristics that may affect both depression and the dependent variables. However, this model does not control for simultaneity (e.g., change in viral suppression leads to lower depression). With multiple time-points, instrumental variable approaches combined with fixed effects potentially can deal with this problem, using baseline depression to predict change in depression from time 2 to time 3, if baseline depression is strongly correlated with change in depression over time. The fixed effects model will indicate important time trends in depression and the primary and secondary outcomes.

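### Secondary Aims 1 & 2: the random effect credited with controlling unobservables most likely does not do so, and the plan leaves open the coding and the estimate that decide whether this matters

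*Combined protocol and SAP*

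**What the plan says.** All the relevant text is in the Data analysis section of the combined protocol and SAP, with the purpose given under Methods.

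- **Purpose.** Methods says that women "who screen positive for potential depression will be enrolled" and then "followed until 18-months post-delivery to assess how depression and depression alleviation relate to primary" and secondary outcomes. Surveys are at baseline and at 6, 12 and 18 months after delivery, so there are four per woman.
- **The claim.** Secondary Aims 1 & 2: "Models will control for observed individual characteristics and unobservables through a random effect term to incorporate characteristics that may affect both depression" and, the sentence goes on, the dependent variables.
- **The admitted limit.** The next sentence names one: "However, this model does not control for simultaneity". Instruments combined with fixed effects are then mentioned as a possible answer to that problem.
- **Fixed effects again.** The section closes: "The fixed effects model will indicate important time trends in depression and the primary and secondary outcomes".
- **The exposure and outcome.** The longitudinal analysis is meant "to explore the relationship between change in depression and outcomes over time", and to test whether alleviation (EPDS 6 or below) "is related to change in these outcomes". No equation is given for these models.
- **The only defined random effect.** In the Primary Aim 1 equation, written for the comparison of arms, theta_i "is an individual-level random effect (to allow for variation across participants").

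**The concern.** A characteristic that affects both depression and the outcome is a confounder. An ordinary random intercept models the correlation among one woman's repeated measurements. It assumes that her intercept is unrelated to the regressors, so it cannot adjust for a trait that drives both depression and adherence. A reader told that unobservables were controlled, and that simultaneity is the only gap, would take stable unmeasured confounding as dealt with.

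Relating depression and its alleviation to the outcomes is a stated purpose of the follow-up and carries a directional hypothesis. If an outcome is modelled as a level, a stable unmeasured trait could appear as a benefit of alleviation.

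**Working it through.** The plan gives no figure for this analysis, so there is none to reproduce. The check is algebra followed by simulation.

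**1. What a random intercept does.** Let depression be d_it = u_i + e_it and the outcome y_it = visit term + beta*d_it + v_i + eps_it, with corr(u, v) = -rho. The random-intercept estimate is approximately

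(W_xy + psi*B_xy) / (W_xx + psi*B_xx), with psi = var(eps) / (var(eps) + T*var(v)),

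where W and B are within-woman and between-woman sums per woman. The within part is free of u and v. The between part is not, and it keeps weight psi.

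Assumed values, not in the documents: beta = 0, variances 1, person share 0.5 for depression and 0.4 for the outcome, no selection at enrolment.

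- T = 4: psi = 0.6/(0.6 + 4*0.4) = 0.273. W_xx = 3*0.5 = 1.5. B_xx = 4*(0.5 + 0.5/4) = 2.5. W_xy = 0. At rho = 0.3, B_xy = -4*0.3*sqrt(0.5*0.4) = -0.537. Estimate = 0.273*(-0.537)/(1.5 + 0.273*2.5) = -0.067, against a true value of 0.
- T = 3 (post-delivery visits only): psi = 0.6/(0.6 + 3*0.4) = 0.333. W_xx = 1.0, B_xx = 2.0, B_xy = -0.402. Estimate = 0.333*(-0.402)/(1.0 + 0.333*2.0) = -0.080.
- Within-woman estimate: W_xy/W_xx = 0 in both cases.

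**2. How coding changes this.**

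- Score or alleviation status against outcome level: the between part enters, as above.
- Change score against outcome level: change is e_it - e_i0, which does not involve u_i. Enrolling women for high baseline depression makes u_i and e_i0 negatively correlated, so some confounding returns.
- Outcome as change from baseline: v_i cancels, and so does the bias from it.

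Where the bias goes, the coding removes it, not the random effect.

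**3. Size in a selected sample.** Linear simulation, 2,000 runs per rho. Further assumptions: 400 women kept if baseline depression exceeds 0.5 SD; nobody alleviated at baseline and 40% afterwards; true effect zero. Entries are false rejection at nominal 5%; ranges cover repeat runs of the same set-up.

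| Coding | rho 0.1 | 0.2 | 0.3 | 0.4 |
|---|---|---|---|---|
| Status v. level, 4 visits | 6-8% | 10-12% | 19-21% | 32-33% |
| Status v. level, 3 visits | 7-8% | 13-15% | 28% | 47% |
| Visit score v. level, 4 visits | 9-10% | 15-19% | 34-37% | 61-63% |
| Change score v. level, 3 visits | 6-7% | 9-12% | 18-20% | 30-31% |
| Change score v. level, 4 visits | 5-7% | 9% | 12-15% | 20-22% |
| Outcome as change from baseline | 4-6% | 4-6% | 4-6% | 4-6% |
| Within-woman term | 4-7% | 4-7% | 4-7% | 4-7% |

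Monte Carlo error is about 1 point near 5% and 2 points near 30-50%. At rho = 0 every coding gives 4-6%. The bias for status over 4 visits is 0.02 / 0.04 / 0.06 / 0.08 SD.

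**4. Other assumptions** (status v. level, 4 visits, rho 0.1 to 0.4).

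- Cut 0 SD: 7 / 14 / 21 / 38%. Cut 1 SD: 6 / 11 / 18 / 30%.
- Shares 0.3 and 0.2: 6 / 11 / 17 / 27%. Shares 0.7 and 0.6: 6 / 10 / 15 / 27%.
- No selection: 9 / 24 / 49 / 75%. Without selection the change score v. level stays at about 5%.
- Binary outcome, 80% prevalence, random-intercept logistic model, 600 runs: 7 / 10 / 16 / 30%, odds ratios 1.06 / 1.14 / 1.26 / 1.33 against a true 1. The within-woman term stays near 5% at rho = 0.

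**The case against.** Four points can be made for the plan.

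1. **The random effect is inferred.** Theta_i belongs to the arm-comparison model. The secondary models have no equation, and a term meant to take in characteristics that affect both variables could be a shared or correlated random effect. This stands as a limit. The ordinary intercept is still the likeliest reading, because the document defines no other.

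2. **The wording leans to a harmless coding.** For alleviation the stated test is whether it "is related to change in these outcomes", and with the outcome as change from baseline the bias disappears. This largely stands. A reader might infer from the larger figures above that the planned alleviation result is biased; the documents do not support that. Nor do they settle the matter: alleviation is a status, the Primary Aim 1 equation has adherence as a level, and the text does not say how change in a binary outcome would be formed.

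3. **Fixed effects are in the plan.** A reader might infer that they are confined to time trends. The closing sentence says that the model will show such trends and sets no such limit. Person fixed effects would remove stable confounding whatever purpose was stated, and in the linear case they equal the within-woman term. But the text does not say that they are person effects, or which estimate carries the conclusions.

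4. **The aim is exploratory and worded as association.** True, and it limits the harm. It does not make a statement about what was adjusted for correct.

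**Conclusion.** The sentence claims more than the defined kind of random effect can deliver. If the secondary models use an ordinary random intercept, confounding by stable woman-level traits is not removed by it under any coding. Whether a coefficient is biased as a result is undetermined, because the coding and the deciding estimate are not stated.

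The size is illustrative only. For status against outcome level over four visits, false rejection runs from slightly above nominal at a residual correlation of 0.1 to about a third at 0.4. It is about 5% if the outcome enters as change or a within-woman term is used. The documents give no residual correlation, variance share, alleviation rate or prevalence, so nothing in them favours the high end over the low end. Only stable confounding was simulated.

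A reader might also infer that the trial's main result is in doubt. It is not: the point concerns the non-randomised secondary aims, and the comparison of arms does not rest on this term. What is at stake is a wrong statement of what was adjusted for, and possibly a spurious secondary finding.

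**What to change.** - Delete the claim that the random effect controls unobservables.
- State how depression and alleviation enter (score, status or change score) and whether each outcome enters as a level or as a change.
- For repeated outcomes analysed as levels, enter each woman's mean depression and her visit-specific deviation, or use person fixed effects. Name that within-woman estimate as the one behind the change-in-depression and alleviation conclusions.
- For outcomes measured once, and for baseline depression (EPDS 13 or above), report covariate-adjusted associations and say that unmeasured confounding is not controlled.
- State that time-varying confounding and reverse causation remain, since the within-woman term does not remove them.

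**Cost.** SAP wording and one added covariate; no new data. Precision falls: under the assumptions above the within-woman standard error is 1.05-1.16 times the random-effects one with four visits, 1.11-1.26 times with three, and up to 1.3 times without selection. Outcomes measured once need only the wording.

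### The alleviation analyses in Secondary Aims 1 & 2 name no study-arm term, so the pooled association can carry part of the intervention effect

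*Combined protocol and SAP*

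**What the plan says.** The Secondary Aims 1 & 2 paragraph under Data analysis sets out three steps.

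- **Bivariate step.** "We will conduct (unadjusted) bivariate analysis to initially examine significant associations between baseline depression" (EPDS ≥ 13), and likewise for alleviation over time, with the primary and secondary outcomes.
- **Longitudinal step.** Repeated observations are used "to test whether depression alleviation" (EPDS ≤ 6) is related to change in outcomes. On adjustment: "Models will control for observed individual characteristics and unobservables through a random effect term".
- **A possible further step.** The one limitation conceded is simultaneity. For that, the plan says that "instrumental variable approaches combined with fixed effects potentially can deal with this problem, using baseline depression to predict change in depression". The instrument is baseline depression, and arm does not appear.

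Arm is specified elsewhere. In the Primary Aim 1 model, "G is binary indicator of treatment group", and the group-by-time interaction is defined as the intervention effect. Nothing carries that term over to Secondary Aims 1 & 2, and no by-arm analysis is described there.

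On treatment, the rationale and Methods place PST and ADT at the 4 experimental clinics. The 4 control clinics use the FSG program and referral to a mental health specialist.

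**The concern.** The second primary aim tests whether depression care beats usual care on adherence, viral suppression and depression alleviation. Arm is therefore expected to act on both sides of the alleviation–outcome association. If some of its effect on outcomes does not run through depression, arm is a common cause, and leaving it out lets the intervention effect appear as an effect of alleviation. The plan makes such a route plausible: its secondary aim lists problem solving skills, which PST targets, as a candidate mediator, and PST brings additional contact with peer mothers.

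At stake is the stated hypothesis that alleviation goes with better adherence, viral suppression and health. Part of an apparent confirmation could come from the arm difference.

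Baseline depression raises a different question. It is measured before treatment, so the issue is whether the pooled association averages two different associations, one under depression care and one under usual care.

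**Working it through.** **The plan's own figure.** 8 clinics × 50 women = 400, as stated; 4 × 50 = 200 per arm. The documents give no rates for alleviation, adherence or suppression, so every rate below is an assumption.

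**Alleviation: expected spurious difference.** Let a₁, a₀ be the alleviation proportions and y₁, y₀ the outcome proportions in the depression-care and usual-care arms. Arms are equal in size, and alleviation has no effect on the outcome within either arm. Pooling the arms gives:

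- outcome among alleviated women = (a₁y₁ + a₀y₀)/(a₁ + a₀)
- outcome among the others = [(1 − a₁)y₁ + (1 − a₀)y₀]/(2 − a₁ − a₀)
- difference = (a₁ − a₀)(y₁ − y₀)/[(a₁ + a₀)(2 − a₁ − a₀)]

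The difference is zero if arm changes only one of the two variables. Both effects are needed.

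Take a₀ = 30% and y₀ = 60%, with a₁ from 40% to 70% and y₁ from 65% to 80%:

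- Smallest: (0.10 × 0.05)/(0.70 × 1.30) = 0.55 points.
- Largest: (0.40 × 0.20)/(1.00 × 1.00) = 8.0 points.

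A second set of assumed rates, with outcome 80% vs 65%:

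- Alleviation 60% vs 40%: 0.6 × 80 + 0.4 × 65 = 74.0 against 0.4 × 80 + 0.6 × 65 = 71.0, or 3 points.
- Alleviation 70% vs 30%: 75.5 against 69.5, or 6 points.

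**Alleviation: false-positive rate of a 5% test.** This was simulated with 20,000 runs, 200 women per arm, no clustering, a₀ = 30%, y₀ = 60% and no within-arm effect. A pooled two-proportion test was compared with an arm-stratified Mantel-Haenszel test.

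| a₁ | y₁ | Spurious difference (points) | Pooled test | Stratified test |
|---|---|---|---|---|
| 40% | 65% | 0.55 | 5.2% | 5.0% |
| 50% | 70% | 2.08 | 6.8% | 4.9% |
| 60% | 75% | 4.55 | 15.7% | 5.1% |
| 70% | 80% | 8.0 | 41.7% | 5.2% |
| 60% | 60% (no outcome effect) | 0 | 5.2% | 5.1% |
| 30% (no alleviation effect) | 75% | 0 | 4.9% | 4.7% |

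**Do the plan's other tools remove this?**

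- A random effect is normally assumed independent of the covariates, so it does not stand in for an omitted arm term.
- Person fixed effects would absorb a constant arm difference but not a differential trend. That trend is what the Primary Aim 1 model calls the intervention effect.
- The instrumental-variable option is only tentative. Its instrument is baseline depression, which at experimental clinics makes treatment contact more likely and so may reach outcomes by that route.

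**Baseline depression.** Assume the same share with EPDS ≥ 13 in each arm, a usual-care gap of D points, and an intervention that removes a fraction k of it. The pooled gap is [D + D(1 − k)]/2 = D(1 − k/2). With D = 15 and k = 25%, 50%, 75% and 100%, it is 13.1, 11.3, 9.4 and 7.5 points. This is averaging over arms, not confounding. It is a separate illustration and is not meant to share rates with the alleviation examples.

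**The case against.** Several points on the other side stand.

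- **The bias is conditional.** It requires arm to change alleviation and also to change outcomes outside depression. The illustrations send the whole arm effect around depression, whereas the trial's rationale expects much of it to run through depression. A reader might infer that the hypothesis would be confirmed by the arm effect alone, but the figures do not show that. In three of the four scenarios with both effects, the pooled test rejects 5.2% to 15.7% of the time, and only the most extreme reaches 41.7%.
- **Control women are not untreated.** A reader might infer that depression is treated in one arm only. Control clinics offer the FSG program and specialist referral, and Methods has women who screen positive receive psycho-education at all sites. Only the PST/ADT package is confined to one arm. The sentence "The PST/ADT treatment will be provided only to study participants, not all depressed clients" does not show even that, since it contrasts participants with non-participants.
- **Baseline EPDS ≥ 13 is not confounded by arm in expectation.** Nor is it the stated trigger for treatment: nurses diagnose depression, and the cut-off appears only as an analysis definition. The pooled association is a legitimate average, and the plan does not say that it seeks the usual-care association alone.
- **The aim is exploratory.** The unadjusted step is only a first look, and longitudinal models follow it.

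One defence does not stand. The phrase about observed individual characteristics could be stretched to cover arm, but arm is assigned by clinic and is not named. That reading also cannot rescue a step labelled unadjusted.

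**Conclusion.** The concern holds for the alleviation analyses as a risk of bias, not as an established bias. As written, neither the bivariate step nor the longitudinal models account for arm, and the tentative fixed-effects and instrumental-variable options would not remove a differential arm trend. Under the assumed rates, with no within-arm effect, the spurious difference runs from 0.55 to 8.0 points. It is close to nil when arm effects are small and material when the intervention works well and partly bypasses depression. The rejection rates ignore clustering.

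For baseline depression the issue is possible effect modification, together with chance imbalance between arms of only 4 clinics each. It calls for by-arm reporting and does not show a biased pooled estimate.

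The primary arm comparison, which has its own group terms, is unaffected. The change should be made before analysis, but the trial's main conclusion does not depend on it.

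**What to change.** Amend the Secondary Aims 1 & 2 paragraph as follows.

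1. Stratify the bivariate alleviation analyses by study arm, giving by-arm results and an arm-stratified summary.
2. Include study arm and arm × time in the longitudinal alleviation models, and in any fixed-effects or instrumental-variable version include at least arm × time.
3. Report the association of baseline depression with outcomes by arm, using an arm × baseline EPDS term. Describe the control-arm estimate as the association under usual care, not as the natural effect of depression, because control women receive support and referral.

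The cost is a few sentences of SAP wording; arm is known for every woman and no new data are needed. By-arm estimates rest on about 200 women each, so with balanced arms and similar variability their standard errors are about √(400/200) = 1.4 times those from all 400. The arm-stratified summary and the arm-adjusted models still use everyone. Adjusting for arm does not make the alleviation association causal: the simultaneity that the plan concedes remains, as does confounding by unmeasured patient characteristics.
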